- SA1: Compare the extent of change pre-test to post-test in walking and mobility outcomes, social and vocational participation, and quality of life between the identical evidence-based individualized exercise program delivered via GEMS-S or GEMS-T in adults with MS who have slowed walking (greater than 6 seconds on the T25FWT);
- SA2: Evaluate and compare the effectiveness between participants randomized to their preferred delivery mode (GEMS-T(Choice) or GEMS-S(Choice)) and those who are not randomized to their preferred delivery mode (GEMS-T or GEMS-S);
- SA3: Evaluate changes in self-efficacy, and adoption of exercise between these groups (GEMS-T, GEMS-S, GEMS-T(Choice), GEMS-S(Choice)).

RESEARCH METHODS

Design

This is a multi-site, 2-staged randomized, choice design study aimed at noninferiority, to compare the effectiveness of delivering an individualized exercise program in a facility (facility-based exercise training or GEMS-S) versus via telerehabilitation (telerehab-based exercise training or GEMS-T) in people with MS. Noninferiority assumes both interventions (GEMS-S and GEMS-T) produce no statistically different outcomes.

Shepherd Center is the Clinical Coordinating site, led by [name], and UAB is the Training Site, led by [name]. UAB will also house the Statistical Center, led by [name]. The Data Management Center led by [name] will be maintained by iConquerMS of the Accelerated Cure Project.

This protocol will first outline site specific procedures and tools, and then will provide details regarding the coordination of the multiple study sites by the investigators at the Shepherd Center.

Participants

We will enroll 400 participants across the following eight centers: The Shepherd Center, Atlanta, GA; the University of Georgia, Athens; the Cleveland Clinic Mellen Center for MS Treatment and Research, Ohio; the University of North Carolina, Chapel Hill; Massachusetts General Hospital, Boston (MGH); the University of Colorado; the University of Alabama, Birmingham (UAB) in collaboration with The Tanner Center and Foundation for Neurological Diseases (Tanner Center); and Marquette University, Wisconsin. The criteria for eligibility will be identical at all sites. Participants will qualify for the study if they meet the following criteria:

Inclusion criteria:

1. Physician-confirmed diagnosis of MS
2. Expanded Disability Status Scale (EDSS) score of 4.0 through 6.5
3. Age between 18 and 65 years

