While trial sites are closed due to the COVID-19 pandemic, no screen 1s, screen 2s, Visit 1s, or associated enrollment activities will take place. Participants currently in the screening and enrollment process, will pause where they are. The recruitment coordinator from the enrolling site will contact those participants and let them know the study is on pause due to the pandemic and that they will be contacted again when enrollment resumes.

- If enrollment resumes past the 60-day screening eligibility window (60 days from screen 2 to visit 1; 60 days from visit 1 to starting exercise), the participant will be rescreened as determined appropriate by the site investigators.

Prescreening activities, such as chart review and preliminary phone calls with interested participants will continue. Interested people will be informed the study is on hold and they will be contacted when enrollment resumes.

Transfer of participant to coach

Once a participant is randomized to their intervention group (GEMS-T or GEMS-S), the research coordinator will provide the respective coach the contact information for the participant. They will also provide the following information:

- If the site PI or RC deems the participant is a fall risk
- The participant's EDSS score
- Whether the participant uses an assistive device

To convey this information to the GEMS-T for the GEMS-T participants, the research coordinators will send an encrypted email to a secure, HIPAA-compliant email address at UAB with this information. This information is to inform the coach of functional status of the participant so that they can modify exercises to prevent falls.

Follow-Up Assessment Procedures

Timing of subsequent outcome assessments are summarized in Table 1. CROs and PROs will be administered again immediately post-intervention (at 16-weeks), and at 12 months post-intervention. PROs will also be assessed at 8-weeks after the start of the intervention and at 6 months post-intervention. Participants will complete their PROs at Visit 1, and 16-weeks, and 12 months post-intervention in a private onsite room with the support of the research staff as needed, with the option of completing the SCT battery at home via the study portal. The research staff will not influence the survey responses but provide technical support to enhance completeness and quality of data. Participants will complete the 8-week and 6-month PROs via the secure online study portal (described below).

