Participants will undertake both aerobic and resistance training of moderate intensity twice per week for 16 weeks (4 months), based on these conditions:

- a. The prescription is individualized, based on each participant's ability. All participants are provided a low-level prescription to try for one week. They are asked to monitor how they feel, and at the end of the first week, they are contacted by a coach (GEMS-S participants in person at the facility; GEMS-T participants via video-chat). The goal is for the participant to gradually progress toward meeting the exercise guidelines.
- b. The elements of the intervention were chosen to facilitate self-management of exercise, as well as to maintain the integrity of the intervention across delivery modes (GEMS-S and GEMS-T). All participants will receive a hip-worn pedometer to monitor steps. This information is to monitor fidelity of the exercise implementation only, and the participant will also record this information on their adherence log for each session. For aerobic training, the walking speed in the natural environment (GEMS-T) are adjusted to get the desired 100 steps/minute and target heart rate (HR) based on HR reserve and target zones

defined by the American College of Sports Medicine.⁴⁴ The target stepping rate and HR correspond to moderate-intensity exercise in persons with MS.

- c. Resistance training consists of 1-2 sets, 10-15 repetitions of 10 exercises targeting lower body, upper body, and core muscle groups performed 2 days per week. Participants start with the amount of resistance at which they can perform 10-15 repetitions. GEMS-T participants will receive bands to use at home, and GEMS-S participants will be given bands to use and keep by each site.
- d. There are three separate levels of difficulty of the exercise intervention (orange, blue, white) that the participant chooses in discussion with their behavioral coach. This mutual decision is based on participants' experience following the first two weeks of the program and coaches' perception of how they did. The levels of difficulty vary in terms of progression toward meeting the exercise guidelines. This feature is critical for accommodating the various levels of ability we anticipate for our participants. Much like those who do not have a disability, each participant may start at a different level; the goal is for each participant to exercise at moderate intensity by week 10 of the intervention.

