If a physician instructs a participant to pause exercising, the site research coordinator must obtain medical clearance from the participant's physician before resuming exercise. If the participant's physician does not instruct a participant to stop exercising, the site PI determines whether or not medical clearance after an AE is required.

Site research coordinators will inform the participant's coaches when medical consent has been obtained and the participant is approved to resume exercising.

Figure 3 below provides additional detail regarding how AEs are reported and addressed.

[figure not shown]
[figure not shown]

Figure 3: AE Reporting and Follow up Procedures

DATA ANALYSIS

Data analysis plan

The primary hypothesis is a non-inferiority test of the changes in T25FWT between GEMS-T and GEMS-S. This will be tested using a linear model with site as the stratification factor and an intention to treat approach. The primary analysis will adjust for covariates age, gender and baseline EDSS or PDDS. Further addition of covariates may be examined in sensitivity analyses based on any differences seen on examination of baseline variables between groups. Secondary endpoints include change in 6MWT and EDSS/PDDS. In all endpoints, we are assessing

improvement over baseline values. We will examine the frequency of worsening as a safety comparison. We will also examine the primary endpoint of a 20% improvement in the T25FWT (yes or no) using logistic regression. Further, to characterize the changes over time, we will use linear mixed models to assess the slopes of change for GEMS-S versus GEMS-T groups. We will also examine the relationship between the dose of exercise measured by compliance and the change in the primary and secondary outcomes. These are exploratory outcomes to see if the compliance measures predict the benefits on the outcomes. This information is important for translation and information dissemination to people with MS.

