Protocol Title: Comparative Effectiveness of an Exercise Intervention Delivered via Telerehabilitation and Conventional Mode of Delivery

Statistical Analysis Plan

PI: [name], Ph.D.

Version: 6/17/2022

Sponsor: Patient Centered Outcomes Research Institute (PCORI)

NCT Number: NCT03468868

Data analysis plan

SA1: Compare the extent of change in walking and mobility outcomes, social and vocational participation, and quality of life. The primary hypothesis is a non-inferiority test of the changes in T25FWT between TET and FET. This will be tested using a linear model with site as the stratification factor included using an intention to treat approach (imputation for missing values are discussed below). The primary analysis will adjust for covariates age, gender and baseline EDSS. Further addition of covariates may be examined in sensitivity analyses based on any differences seen on examination of baseline variables between groups. Secondary endpoints include change in 6MWT and EDSS. In all of these endpoints we are looking at improvement over baseline values whereas many MS studies focus on worsening. We will examine the frequency of worsening as a safety comparison. We will also examine the primary endpoint of a 20% improvement in the T25FWT (yes or no) using logistic regression. Further, to characterize the changes over time, we will use linear mixed models to assess the slopes of change for FET versus TET groups. We also will examine the relationship between the dose of exercise measured by compliance and the change in the primary and secondary outcomes. These are exploratory outcomes and will be assessed with no corrections for multiple testing and are important mostly for descriptive analyses to see if the compliance measures indeed predict the benefits on the outcomes as this information is important for translation and information to people with MS.

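### Comparing slopes between modes suits poorly a programme that ends at week 16 with walking tests only at baseline, 16 weeks and 12 months later; compare the modes at each visit instead.

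*SAP*

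**What the plan says.** In SA1 of its *Data analysis plan*, the SAP supplements the primary analysis with a description of the course over time: "we will use linear mixed models to assess the slopes of change for FET versus TET groups". The protocol's *Data analysis plan* has the same plan under its own labels: "we will use linear mixed models to assess the slopes of change for GEMS-S versus GEMS-T groups". (FET and GEMS-S are the facility mode; TET and GEMS-T are the telerehabilitation mode.) Neither document says whether time is continuous or categorical, whether there is a knot, which visits enter, or which random effects or covariance are meant.

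The schedule is in the protocol's *Follow-Up Assessment Procedures*: "CROs and PROs will be administered again immediately post-intervention (at 16-weeks), and at 12 months post-intervention". Two more visits collect patient-reported outcomes (PROs) only: "PROs will also be assessed at 8-weeks after the start of the intervention and at 6 months post-intervention". Table 1 agrees: T25FWT, 6MWT and EDSS have no 8-week or 6-month assessment. The *Intervention* section sets a 16-week programme, so the 16-week visit falls where the programme ends.

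The main comparison is separate from the slopes: "The primary hypothesis is a non-inferiority test of the changes in T25FWT between TET and FET". The protocol's SA1 sets its aim as "Compare the extent of change pre-test to post-test in walking and mobility outcomes".

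**The concern.** The follow-up has two phases that meet at week 16: the programme, then a year without it. A mode could gain in the first phase and hold, lose or extend that gain in the second. One slope per mode reduces both phases to a single number, and the unequal spacing puts most of the weight on the last visit.

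What is at stake is the supportive longitudinal comparison. Readers will look there to see whether either mode's gain lasts, and the analysis sections name no explicit 12-month contrast elsewhere. A slope could hide a real gain at the end of treatment and, in some configurations, rank the modes differently from their visit means. Leaving the time coding open also lets it be chosen after the data are seen.

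**Working it through.** The plan gives no figure for this analysis, so there is none to reproduce.

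**Inputs.** Clinician-rated visits at weeks 0, 16 and 68 (16 + 52), from the protocol's follow-up section. Table 1 heads the column only as 12 months, so week 52 is run as an alternative. Trajectories and SDs below are assumptions. A negative change in T25FWT is an improvement.

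**1. Weight of each visit.** With complete data and a random intercept (with or without a random slope), the fitted slope is the sum of visit means times (t − t̄)/Σ(t − t̄)².

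- Weeks 0/16/68: t̄ = 28; deviations −28, −12, +40; sum of squares 784 + 144 + 1600 = 2528. Weights × 52, per year: −0.576, −0.247, +0.823.
- Weeks 0/16/52: weights per year −0.831, −0.244, +1.075.

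The 16-week weight is negative in both cases. With the other visits fixed, a larger gain at the end of treatment makes the slope look worse.

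**2. One mode's own slope.** Let the gain be g at week 16 and let a fraction r of it be kept at the last visit, so the changes are (0, −g, −rg). For week 68 the slope is g(12 − 40r)/2528 per week.

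- It is zero at r = 12/40 = 0.30; below that the slope shows worsening.
- For week 52 the zero is at r = 0.244/1.075 = 0.227.
- A 1 s gain that is fully lost gives 12/2528 = +0.00475 s/week, or +0.25 s/year.

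**3. Two modes.** Let mode A's advantage over B be a₁₆ at week 16 and a_last at the end, with equal baselines. The week-68 slope difference, A minus B, is (12a₁₆ − 40a_last)/2528. A looks worse only if a₁₆ > (40/12)a_last = 3.33 a_last. For week 52 the factor is 1.075/0.244 = 4.4. If the two trajectories are the same, the difference is zero whatever their shape.

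**4. Assumed example.** A changes by −2.0 s then −0.4 s; B by −0.5 s then −0.2 s. A is better by 1.5 s and then by 0.2 s, a ratio of 7.5.

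| Last visit | Slope A (s/year) | Slope B (s/year) |
|---|---|---|
| Week 68 | (24 − 16)/2528 × 52 = +0.165 | (6 − 8)/2528 × 52 = −0.041 |
| Week 52 | +0.059 | −0.093 |

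The slope ranks A worse although A is better at both visits. With 200 per mode and assumed SDs of 2.5 s between persons and 1.2 s residual, simulation gave the wrong order in 95% of runs (week 68) or 84% (week 52). The example was chosen to show the mechanism; these rates do not estimate the risk in this trial.

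**5. Other covariance structures.** The 16-week weight per year was:

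- −0.584 (week 68) or −0.614 (week 52) under AR(1) by visit with correlation 0.9;
- between −0.03 and −0.22 with a common baseline and correlations of 0.5 to 0.9;
- −0.001 to −0.002 under exponential correlation in time, where the visit is practically ignored.

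The thresholds move accordingly. Under AR(1) at week 68, the own-slope threshold in step 2 becomes 0.584/0.902 = 65%. With a common baseline at week 68, the factor in step 3 lies between 0.816/0.219 = 3.7 and 0.784/0.083 = 9.4.

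**6. PROs.** With five visits at weeks 0, 8, 16, 42 and 68, the 16-week weight is −10.8/3116.8 × 52 = −0.180 per year. With weeks 0, 8, 16, 26 and 52 it is −0.141.

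**The case against.** The strongest reply has four parts.

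- **The wording names a model class.** A linear mixed model can have categorical or piecewise time, and neither document prescribes a straight line. This stands as a limit. Still, slopes of change most naturally means one line per mode, and no alternative is stated.
- **The 16-week comparison is already planned.** The SAP has models for change in T25FWT, 6MWT and EDSS, a 20% responder analysis and a worsening comparison, and SA1 refers to change from before to after the programme. This also stands. A reader might infer that the slope is the plan's only comparison of change between modes, but the documents show otherwise. What they lack is an explicit 12-month contrast.
- **Fading is not predicted.** The programme is built to support self-management, and adoption of exercise is one of its aims. The main hypothesis is similar improvement in both modes, in which case the slope difference is near zero. This stands, so the harm is conditional. The loss of separation between the two phases does not depend on fading.
- **The slope is descriptive.** The SAP's exploratory label follows the dose-compliance sentence, and it is unclear whether it covers the slopes. Their role is supportive either way. A descriptive analysis should still be able to show the shape it describes.

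**Conclusion.** The concern holds in a limited form. On the natural reading, the slope comparison is a poor summary for this schedule: the 16-week visit gets a negative or practically zero weight under every structure tried, so the line cannot separate treatment-phase gain from later course. A mode's own slope shows worsening below 30% retention (about 23% for week 52). A mode better at both follow-up visits is ranked worse only when its early advantage exceeds about 3.3 times its final one (4.4 times for week 52).

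These thresholds assume complete data and a random intercept. They change with the covariance structure, and with missing visits, since the protocol's *COVID-19 Follow-up Assessment Procedures* suspend T25FWT, 6MWT and EDSS during site restrictions.

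Two stronger readings are tempting. A reader might infer that retention below 30% reverses the ranking of the modes; that follows only against a mode with no effect at any visit. A reader might also infer that the trial's main conclusion is at risk. It is not: the primary non-inferiority test, the responder analysis and the secondary change analyses do not use the slope.

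**What to change.** Replace the slope comparison in both documents with a mixed model that has:

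- visit as categorical: baseline, 16 weeks and 12 months post-intervention for clinician-rated outcomes, and all five visits for PROs;
- a mode-by-visit interaction and unstructured covariance, with the handling of baseline stated.

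Report the mode difference with 95% CI at 16 weeks and at 12 months post-intervention. In the assumed example this returns −1.5 s and −0.2 s, which is the correct order at both visits.

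No new data are needed, only a change of wording in the SAP and the protocol. Against one line per mode, the model has one extra mean per mode for clinician-rated outcomes (3 − 2) and three for PROs (5 − 2). Unstructured covariance needs 3 × 4/2 = 6 or 5 × 6/2 = 15 parameters. That is small with about 400 participants.

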4. Able to travel to a GEMS-S site for testing and training
5. Accessible, technological platform for GEMS-T (i.e. computer or DVD player and TV,

and telephone)

6. A score of between 25 and 75 on the MSWS-12
7. Timed 25-foot walk test (T25FWT) time of between 6 seconds and 3 minutes
8. Medically stable or approval from physician to participate in exercise studies
9. A score of between 3 and 6 (inclusive) on the Patient Determined Disability Steps

Exclusion criteria:

1. Documented MS relapse in the past 30 days
2. Have had falls in the past three months that the study investigator determines makes participation unsafe
3. Unable to walk 25 feet
4. Already exercises at recommended levels as determined by a score of 25 or higher on the Godin Leisure-Time Exercise questionnaire
5. Has other neurological (e.g., stroke) or musculoskeletal conditions or other co-morbidities
6. Has cognitive difficulties as determined by a Mini Mental Status Exam score <19
7. Is not proficient in English
8. Is physically unable to complete the second T25FWT trial
9. Any other concern that the investigators deem would jeopardize the safety of the potential participant.

We will randomize 200 participants to the Choice group and 200 to the No Choice group. Those in the Choice group will choose which exercise program to undertake – GEMS-T or GEMS-S. In the No Choice group, we will randomize 100 participants to GEMS-S and 100 to GEMS-T (see Figure 1). Four sites (Shepherd Center with help from UGA, Marquette University, Cleveland Clinic, and University of Colorado) will each recruit 80 participants. UNC and MGH will together recruit a total of 40 participants. UAB will recruit at least 40 participants with help from the Tanner Center, a Birmingham-based multidisciplinary center providing neurology, nursing, infusion, clinical research, neurodiagnostic testing, occupational therapy, physical therapy, speech/language pathology, licensed professional counseling, group wellness classes, and individual personal training in one central location.

[figure not shown]

Figure 1: Randomization Scheme for Each Participant

Recruitment methods

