Multiple Sclerosis Impact Scale-29	A 29-item self-report of participant's views on the impact of MS on day-to-day life during the past two weeks.				X	X	X	X	X
Social Cognitive Battery	See Table 2.				X	X	X	X	X
Participant Feedback Survey	27-item survey obtaining participants' feedback with the exercise program to assist with program modification and post-study dissemination.					X			

Adherence log is maintained weekly by participant to evaluate fidelity of the intervention across groups, as well as measure adherence with the protocol.

Reason for group choice: If randomized to the choice group, the research coordinator will complete the Choice form, which asks questions to determine if the COVID pandemic influenced their decision-making process. If not administered at randomization, the Choice form will be completed at 16 weeks.

Table 2. Social Cognitive Theory Battery	
Tool	Description
Exercise Self Efficacy Scale⁷⁸	10-item Likert scale measuring an individual's self-efficacy to undertake exercise related tasks and overcome barriers related to exercising.
Exercise Goal Setting Scale⁷⁹	10-item Likert scale assessing the extent an individual sets exercise goals.
Multidimensional Outcome Expectancies for Exercise Scale⁸⁰	19-item Likert scale measuring an individual's beliefs or expectations about the benefits of regular exercise or physical activity.
Exercise Barriers	8 questions to measure an individual's beliefs about the barriers related to exercising.
Social Provisions Scale⁸²	6-item scale measuring the degree to which respondent's social relationships provide various dimensions of social support in relation to physical activity.
Physical Activity Self-Regulatory Scale⁸⁴	12-item scale measuring an individual's self-regulation in relation to exercise.
Barriers for Self-Efficacy	13-item scale measuring individual's self-efficacy to participate in exercise when encountering barriers.

Once all baseline outcome measures are obtained, participants will be randomized and notified soon after by the site research coordinator of their group assignment. Randomization completes enrollment.

COVID-19 Screening and Enrollment Procedures

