SA2: Evaluate and compare the effectiveness between participants randomized to their preferred delivery mode (TET(Choice) or FET (Choice)) and those who are not randomized to their preferred delivery mode (TET or FET). For this aim we will use the same models as the primary but examining and interaction term for Choice and treatment and contrasts will be conducted comparing the four cells. We will assess if the effect of Choice is the same for both treatments. Logistic regression will be used to assess the interaction between choice and adherence and attendance or dropouts. We also will examine time to dropout and/or time until dropout or poor compliance (which will be defined prior to final analyses). We also are interested in examining the intensity or compliance of the intervention to the choice as well as impact on the primary endpoint as noted above.

SA3: Evaluate changes in self-efficacy and adoption of exercise between these groups (TET, FET, TET(Choice), FET(Choice)). Self-efficacy and adoption of exercise are discussed above and use the same models and approach. We will also utilize mediation analyses to understand if the changes induced by exercise are mediated via the changes in self-efficacy. Here we will use the approach by MacKinnon built on Judd and Kenny.⁷⁹⁻⁸⁴ Analyses of the MSWS-12, MFIS, and the NeuroQOL will all be analyzed using regression models similar to the timed walk models above and will utilize the same contrasts for examining choice as well as treatment effects.

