Data linkage plan. Each participant will be assigned a study ID number when randomized to the intervention group by the biostatistician. This will be the only identifier in all databases and systems used in this study. The Shepherd Center will maintain the master file. None of the investigators or staff involved in the assessments will have access to the identifier data, and thus will remain blinded to the assignment for the entire intervention phase.

Sensitivity analyses. Randomization should balance covariates across treatment groups, but this will be checked with frequency and means tables, and chi-square/Fisher exact and F-tests/t-tests respectively. If treatment groups show important imbalances among covariates, then they can be adjusted for using covariates in various types of regression models as we noted above under the primary analyses. As noted briefly in the primary analysis section, per protocol analyses will be used to support the conclusions of the intention to treat analyses. In the intention to treat analyses we must take into account dropouts. For anyone with at least one post randomization timed walk test, we will impute a model based final endpoint to assess change. Key sensitivity analyses will include adjustment for covariates: age, gender, sex and treatment preference at entry. Interaction terms will be used to identify potential impacts of key covariates. In addition, imputation for missing values will be conducted to assess the impact of these lost observations. We note again that rules are in place to deal with the time variables. For other variables (MSWS, MFIS and NeuroQOL, EDSS) will require various forms of imputation for sensitivity analyses. We will use a general approach discussed below for imputation of these secondary endpoints and use per protocol versus ITT for sensitivity analysis. For the major analyses, best case and worst case analyses will be done. Subgroup analyses will attempt to quantify the consistency of the findings amongst subgroups.

Management of missing data

a. Methods to prevent and monitor missing data.

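### SA2 is labelled as preferred versus non-preferred mode, but the design compares choice with no choice, and no listed form records the preference covariate that the SAP relies on

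*SAP*

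**What the plan says.** The Protocol (Participants) gives the allocation: "We will randomize 200 participants to the Choice group and 200 to the No Choice group". For the first group, "Those in the Choice group will choose which exercise program to undertake". For the second, "In the No Choice group, we will randomize 100 participants to GEMS-S and 100 to GEMS-T".

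SA2 describes these groups differently. Both the Protocol (Specific Aims) and the SAP (Data analysis plan) present the Choice cells as people randomised to the mode they prefer. The comparison group is "those who are not randomized to their preferred delivery mode (GEMS-T or GEMS-S" in the Protocol and "those who are not randomized to their preferred delivery mode (TET or FET" in the SAP, where TET and FET are the SAP's names for GEMS-T and GEMS-S. The SA2 analysis is the primary model with "examining and interaction term for Choice and treatment and contrasts will be conducted comparing the four cells".

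On preference as a variable, the SAP (Sensitivity analyses) says: "Key sensitivity analyses will include adjustment for covariates: age, gender, sex and treatment preference at entry". The only related form appears in the Protocol below Table 1: "If randomized to the choice group, the research coordinator will complete the Choice form". It is described as asking whether the pandemic influenced the decision, and it may be completed at 16 weeks if it was not done at randomisation.

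**The concern.** Neither half of the SA2 description fits the design. Choice participants are not randomised to a mode; they select one. No Choice participants are assigned a mode by chance, so that group mixes people who got what they would have chosen with people who did not.

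Entry preference is the variable that would separate the two, and the SAP calls for it in a key sensitivity analysis. No listed form supplies it for No Choice. In Choice it can only be inferred from the mode selected, so it carries no information beyond mode.

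Two things are at stake. A choice-offer contrast could be reported as a preference-match contrast, so that a null result is taken to mean that preference is unimportant. And a pre-specified adjustment could not be run from the data described.

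**Working it through.** **Allocation.** 200 + 200 = 400 and 100 + 100 = 200, so the plan's own figures agree. The documents give no power calculation, alpha, SD or effect size for SA2. Those inputs are assumed below.

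**Where preference could be recorded.** Table 1 has no preference item at Screen 1, Screen 2, Visit 1 or Enrollment. Its demographics row is itemised and omits preference, and Table 2 (the social cognitive battery) has none. Randomisation follows the baseline measures. The Choice form comes after randomisation and covers the Choice group only.

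**Matched share in No Choice.** Let p be the share preferring telerehab among those with a preference, and u the share with none.

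- Matched share = 0.5·p(1−u) + 0.5·(1−p)(1−u) = (1−u)/2.
- u = 0 gives 50% (100 of 200) for any p. The 95% chance range (hypergeometric) is 86 to 114 at p = 0.5 and 88 to 112 at p = 0.8.
- u = 10%, 20%, 30%, 50% gives 45%, 40%, 35%, 25%.
- The share differs by cell. With u = 0 and p = 0.7, it is 70% in No Choice telerehab and 30% in No Choice facility.

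**What pooled Choice v No Choice estimates.** Let δ be the effect of being matched, let choosing itself add nothing, and let u = 0. Choice contains δ and No Choice contains 0.5δ, so the difference is 0.5δ. If p differs from 0.5, the mode mix also differs between the groups, which adds (p − 0.5) × (telerehab minus facility effect). That term vanishes if the modes perform alike on average.

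**What the within-mode contrasts estimate.** Telerehab (Choice) minus telerehab (No Choice) equals (1−p) × (telerehab-preferrers on telerehab minus facility-preferrers on telerehab). The facility contrast has factor p. Each therefore combines matching with any prognostic difference between preference types. At p = 0.7 the factors are 0.3 and 0.7, so the Choice effect can differ between modes even when δ is the same in both.

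**Illustrative power.** Assumptions: SD 1, two-sided 5%, no dropout, u = 0, normal approximation, power = Φ(effect/SE − 1.96).

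- Choice v No Choice: effect δ/2, SE = √(1/200 + 1/200) = 0.100.
- Match effect within No Choice, adjusted for preference and mode: effect δ, SE = 0.5·√(sum of 1/n over four cells), with 100p and 100(1−p) people in each mode. SE = 0.141, 0.154 and 0.177 at p = 0.5, 0.7 and 0.8.

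| δ (SD) | Choice v No Choice | Within No Choice, p = 0.5 | p = 0.7 | p = 0.8 |
|---|---|---|---|---|
| 0.3 | 32% | 56% | 49% | 40% |
| 0.4 | 52% | 81% | 74% | 62% |

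For δ = 0.4 and p = 0.7: 0.4/0.1543 − 1.96 = 0.63, and Φ(0.63) = 0.74. The advantage disappears when the SE reaches 0.2, that is, when p(1−p) = 0.02/0.16 = 0.125, or p of about 0.85.

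**The case against.** The best defence is that Choice versus No Choice is a valid randomised comparison. The Protocol's background states the secondary hypothesis against no-choice conditions, and its Data analysis plan does not attach the non-preferred label to the two No Choice cells. An average preference effect can even be derived without individual data. With p and the chosen-mode mean taken from Choice, the mismatched mean on telerehab is (No Choice telerehab mean − p × Choice telerehab mean)/(1−p). This stands, but it assumes that choosing has no effect, and the SAP specifies no such estimator.

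A reader might go further than the documents allow in four ways:

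- **That the missing item causes the mixing.** It does not. Randomisation without regard to preference causes it; recording preference would only show who is matched.
- **That preference is certainly never recorded.** The appended forms and the full Choice form are not shown, and the SAP gives a general assurance that needed covariates will be collected. What can be said is that no instrument is listed.
- **That Choice is fully matched.** The Choice form itself allows that the pandemic swayed decisions, and some facility participants moved to remote exercise during closures. Selected mode may therefore differ from entry preference or from what was received.
- **That the main result is at risk.** Preference enters only a sensitivity analysis. The SAP's primary model adjusts for age, gender and baseline EDSS.

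**Conclusion.** The SA2 label does not fit the design, and the entry-preference adjustment cannot be run from the data that the documents list. About half of No Choice is expected to be matched, or (1−u)/2 where some people have no preference. Pooled Choice versus No Choice then carries about half of any match effect, provided that everyone has a preference, choosing adds nothing and the modes perform alike on average.

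The power figures are illustrative. They depend on an effect size and alpha that the documents do not give, and the 81% is the best case of an even preference split. The contrast is mislabelled rather than useless. Severity: should-fix.

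**What to change.** 1. In SA2 of the Protocol's Specific Aims and of the SAP, name the groups Choice (mode selected) and No Choice (mode assigned). Interpret pooled Choice versus No Choice as the effect of offering a choice. Do not call No Choice non-preferred, and do not read a null result as showing that preference is unimportant.
2. Delete entry preference from the sensitivity covariates, or name the form that records it for every participant before randomisation.
3. For anyone not yet randomised, add one item to the Enrollment column of Table 1 (facility, telerehab or no preference). Estimate the match effect within No Choice, adjusted for preference and mode.

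Steps 1 and 2 cost only wording, and they are the only steps open for waves already enrolled. With the SAP dated 6/17/2022, that may be most or all participants. Step 3 costs one survey item. Its small downside is possible disappointment among people who state a preference and are assigned the other mode.
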